Click in the appropriate box See the "Guide for Investigators" for definitions and further information.

NA – institution is not a covered entity

NA – will not use or disclose protected health information

- HIPAA authorization will be obtained
- An application for waiver/alteration of HIPAA authorization will be submitted

Appendix A: Clinical Questionnaire

Have you experienced in the last 24 hours any:

1. Chest pain
2. Shortness of breath
3. Dizziness, lightheadedness, clamminess, diaphoresis (sweating), or fatigue
4. Nausea, vomiting, belching, or indigestion
5. Extremity swelling, pain, warmth, erythema
6. Difficulty speaking, walking or understanding language
7. Paralysis, numbness, or weakness of the face, arm, or leg
8. Vision or hearing changes
9. Headache
10. Alteration in mental status (including, but not limited to confusion, memory loss, disorientation, or loss of alterness)
11. Fever or chills
12. Cough
13. Itching
14. Skin abnormalities to include, but not limited to rash or blistering
15. Depression Symptoms:
 - a. Depressed mood
 - b. Loss of interest or pleasure
 - c. Change in appetite or weight
 - d. Sleep disturbance(s)
 - e. Psychomotor disturbances (i.e. hand wringing, pacing, or fidgeting; slowness in body movements, thinking or speech)
 - f. Feelings of worthlessness or guilt
 - g. Thoughts about harming yourself or others

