Erythropoietin Injections (Credentialled procedure): A dose (50 IU/kg body mass) of recombinant human EPO (PROCRIT, EPOETIN ALFA, Janssen Products, LP, Titusville, NJ, USA) will be injected subcutaneously 3 times per week for 4 week. Injections will be performed by credentialled study staff at USARIEM. The Office of Medical Support and Oversight (OMSO) will be the prescriber of prescription drugs used in this protocol, to include EPO. The dosing amount and frequency is on-label dosing equivalent to pediatric dosing. This dose and duration has previously been shown to be sufficient to result in hematological adaptions and increase physical performance (18, 19, 33). Hematocrit and hemoglobin will be checked weekly to ensure values remain $< 50\%$. If Hct increases above 50%, EPO injections will be stopped and Hct will be reassessed within 3 days. If hemoglobin increases more than 1 g/dL over a 1 week period EPO injections will be stopped and hemoglobin will be reassessed within 3 days. Reticulocyte count will also be assessed on the first injection day, then again during week 2 and 4 of the injection phase. Additionally, before starting prescribed exercise, volunteers will complete a short clinically relevant health questionnaire and have vital signs checked (blood pressure, heart rate, and SpO_2) which will take about 5 minutes by study staff. Copies of all health related information will be provided to the OMSO daily for review and tracking. After the final injection volunteers will continue to be

monitored for 2 weeks by participating in weekly blood draws and daily monitoring of vital signs and health questionnaire which will continue to be reviewed by OMSO. Study personnel conducting this procedure will be credentialed and listed on the DOA log with code "F."

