Study Exercise (non-credentialed procedure): During the injection phase volunteers will conduct prescribed exercise training 4 days and 1 day of physical performance testing (time trial) per week. Volunteers will perform both weighted (treadmill or outdoor; walking, running, and load carriage) and unweighted (cycle ergometry) endurance-type exercise, and resistance-type exercise throughout the protocol. Exercise will be metabolically matched between groups, with exercise-induced energy expenditure being 1000-1500 kcal per day. Prescribed endurance-type exercise will be low-to-high intensity (30-85% $\dot{V}O_2$ peak) using the ACSM metabolic equations for steady-state exercise (37) and the compendium of metabolic equivalents for physical activities. This level of training is similar to that conducted during arduous military training in garrison (38). $\dot{V}O_2$ peak will be assessed after 2 weeks into the injection phase. Exercise intensity will be adjusted based on alterations in $\dot{V}O_2$ peak. Study personnel conducting exercise will be listed on the DOA log with code "V."

Load Carriage Exercise (non-credentialed procedure): Volunteers will complete 90-min of weighted steady-state exercise on a treadmill at $55 \pm 5\%$ of their $\dot{V}O_2$ peak, with 30% of volunteer's body mass. The speed and grade of the treadmill will be determined using the ACSM metabolic equation for walking based on desired $\dot{V}O_2$ (39). Prior to the protocol day, participants will perform a practice session of the treadmill exercise to confirm the prescribed speed and grade are appropriate to induce target $\dot{V}O_2$. The treadmill speed and grade will be maintained for both arms of the study to match the absolute workload of the exercise across treatments. Study personnel conducting treadmill load carriage will be listed on the DOA log with code "V."

Carbohydrate Tracer Study (credentialed procedure): Following an overnight (10 hour) fast, two catheters will be placed into the lower arm (one in each arm). One arm will be used for infusion of 6,6-[2 H₂] glucose tracer and the other will be used for blood sampling. Following an initial blood sample collection to determine background enrichments, a primed, continuous infusion of 6,6-[2 H₂] glucose will begin (prime, 82.2 $\mu\text{mol}\cdot\text{kg}^{-1}$; continuous rate, 0.78 $\mu\text{mol}\cdot\text{kg}^{-1}\cdot\text{min}^{-1}$, **Figure 4**). The 6,6-[2 H₂] glucose will

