Volunteers will be medically cleared by the OMSO before participation in accordance with USARIEM procedures outlined for screening volunteers for research involving exercise, tracer infusions, muscle biopsies and EPO use at USARIEM. In addition, volunteers will be screened for problems with blood clotting, including prothrombin time (PT)/ partial thromboplastin time (PTT), which is a specific criterion for research involving muscle biopsies. Health problems identified during the screening process will be documented and a copy provided to the volunteer. The volunteer will be encouraged to make an appointment with their primary care provider for a full evaluation of the problem. Volunteers with evidence of any physical, mental, and/or medical conditions that would make the proposed studies relatively more hazardous will be excluded. Any personal health information collected during this screening process will be destroyed at the time of study withdrawal or at the completion of the study.

All volunteers must be willing to consume only food and beverages provided by study staff during the entire study. Additionally, volunteers must be willing to refrain from any additional exercise during the study.

C1.4 Consent Process

Informed consent documents will be provided to each prospective volunteer. Additionally, an oral presentation will be provided to prospective volunteers by the principal investigator or his designee. In case of COVID risk mitigation plans, briefings can be done virtually and consent forms can be emailed and digitally signed. The purpose of this study, procedures involved, risks, and expectations of volunteers will be explained. The principal investigator or designee will answer all group and private

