Measures to Minimize Risks of Harm: To minimize side effects the study will use a low dose EPO injection equivalent to a pediatric dose. Before participants begin the prescribed exercise they will complete a short clinically relevant health questionnaire (**Appendix A**) and have their vital signs (blood pressure, heart rate, and SpO₂) assessed by study staff. Copies of all health related information will be provided to OMSO daily for review and tracking. Hemoglobin and Hct values will be measured weekly during EPO injections. To minimize risk of blood clots Hct values will be maintained < 50%. If Hct values increase > 50% EPO injections will be stopped. Volunteer will return to for another Hct check within 3 days. If hemoglobin increases more than 1 g/dL over a 1 week period EPO injections will be stopped and hemoglobin will be reassessed within 3 days. EPO injections will only be administered by credentialed staff at USARIEM. These individuals will follow administration procedures provided in the PROCRIT® prescriber information guide. Volunteers will continued to be monitored for 2 weeks after the injections are complete to ensure there are no complications from the EPO injections. The OMSO will be responsible for observing and monitoring adverse events of participants in this study.

Research Procedure Name: Exercise

Research Procedure Description: Exercise testing will occur on a cycle ergometer or treadmill. Exercise will be at various levels of intensity based on exercise protocol.

Research-related Risks: Exercise per se rarely provokes cardiovascular events in healthy individuals with normal cardiovascular systems. The prevalence of fatal events in the U.S. is approximately 1:133,000 to 1: 185,000 for men and 1:769,000 to 1:1,500,000 for women who are competitive high school and college athletes. For middle-aged and older adults the relative risk rises to 1:15,000 to 1:18,000 for individuals without a prior history of cardiovascular events. Current civilian and military guidelines state that individuals less than 40 years of age who have no symptoms of or known presence of heart disease or major coronary risk factors have a low risk for cardiac

complications during vigorous exercise. All volunteers in this study fall into this low risk category. Local muscle discomfort and fatigue may occur in active muscles during and shortly after exercise. Muscle soreness, ranging in intensity from mild to severe, may persist for 1 to 7 days.

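### In the injection phase the symptom questionnaire is required on about five days a week but looks back only 24 hours, so about 48 hours of an ordinary week are never asked about

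*Protocol*

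**What the plan says.** Four parts of the protocol bear on this.

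- **When the check is done during dosing.** B5.3 (Erythropoietin Injections) states that "before starting prescribed exercise, volunteers will complete a short clinically relevant health questionnaire and have vital signs checked". C6.1 (Exogenous EPO) repeats the trigger among the measures to reduce EPO risk: "Before participants begin the prescribed exercise they will complete a short clinically relevant health questionnaire". The visible text gives no other trigger for the injection phase. The weekly safety blood draw described under Blood Sampling has no questionnaire attached.
- **How often exercise occurs.** B5.3 (Study Exercise): "During the injection phase volunteers will conduct prescribed exercise training 4 days and 1 day of physical performance testing (time trial) per week". C1.3 adds that "volunteers must be willing to refrain from any additional exercise during the study", so the remaining days bring no exercise-triggered check.
- **What the form asks.** Appendix A: "Have you experienced in the last 24 hours any", followed by a list that includes chest pain, limb swelling, speech difficulty, weakness and headache.
- **What happens after dosing.** For the two weeks after the final injection, B5.3 (Erythropoietin Injections) specifies "daily monitoring of vital signs and health questionnaire which will continue to be reviewed by OMSO".

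The same B5.3 paragraph sends health information to the medical office (OMSO) each day. That governs transfer of what has been collected. It does not say that a form is completed every day.

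**The concern.** A look-back of 24 hours gives continuous symptom coverage only if the form is completed every day. The stated trigger gives about five completions a week, so the look-back is shorter than some of the intervals between forms. A symptom that begins and resolves after one check, and more than 24 hours before the next, is never asked about.

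This matters because C6.1 names the check as one of the measures to minimise EPO risk. The Appendix A items correspond to risks listed there: blood clots, raised blood pressure, headache, myocardial infarction and stroke. With only 8 volunteers needed to complete, each solicited symptom carries weight. The protocol also writes daily checks for the period after EPO stops but not for the period in which it is given, so the intended frequency during dosing is unclear.

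**Working it through.** The plan states no count of monitored days, so there is no figure of its own to reproduce. The check is a count.

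**Inputs**
- Injection phase: "injected subcutaneously 3 times per week for 4 week" (B5.3, Erythropoietin Injections), that is 4 × 7 = 28 days and 3 × 4 = 12 injections.
- Check days per week: 4 training + 1 time trial = 5, or 4 if the time trial is not prescribed exercise (B5.3, Study Exercise).
- Look-back per check: 24 hours (Appendix A).
- Start of daily checks: after the final injection (B5.3, Erythropoietin Injections). The weekday is not given.

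**One ordinary week**
- Five checks: covered at most 5 × 24 = 120 h; uncovered 168 − 120 = 48 h.
- Four checks: covered at most 4 × 24 = 96 h; uncovered 168 − 96 = 72 h.

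The weekly totals do not depend on where the free days fall, if checks are at the same hour. Irregular hours cannot raise coverage above the maximum.

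**Whole phase, daily follow-up starting after week 4**
- Five a week: 28 − (5 × 4) = 8 days without a check, 8/28 = 29%.
- Four a week: 28 − (4 × 4) = 12 days, 12/28 = 43%.

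**Sensitivity to the start of daily follow-up.** All weekly placements of the check days were enumerated, counting days without a check and 24-hour blocks outside every look-back.

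| Checks per week | Daily follow-up from | Days without a check | 24-h blocks uncovered |
|---|---|---|---|
| 5 | day 29 | 8 | 7–8 |
| 5 | day 28 | 7–8 | 6–8 |
| 5 | day 27 | 6–8 | 6–8 |
| 4 | day 29 | 12 | 11–12 |
| 4 | day 27 | 10–12 | 9–12 |

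For example, with exercise Monday to Friday, a final injection on day 26 and daily checks from day 27, both counts are 6.

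**Where the gap falls.** Suppose checks are at 08:00.
- Consecutive free days, with checks on Friday and Monday: Monday's form reaches back to Sunday 08:00. The gap runs from Friday 08:00 to Sunday 08:00, 48 h.
- A single free day, with checks on Monday and Wednesday: Wednesday's form reaches back to Tuesday 08:00. The gap runs from Monday 08:00 to Tuesday 08:00, 24 h. A second such day in the week again makes 48 h.

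Much of the uncovered time therefore follows an exercise-day check and does not lie on the free day.

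**The case against.** The best defence is that daily checks were intended throughout. The injections paragraph sends information to OMSO daily during dosing, then says monitoring will *continue* afterwards, which suggests one regime carried forward. Figure 3 and the Appendix F timeline could not be seen and may settle it. This stands as evidence of possible intent, and it rules out reading the text as a deliberate choice to watch volunteers less closely while EPO is given. It does not supply a rule for non-exercise days.

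A second defence is that adverse-event capture does not rest on this form. C7.1 has adverse events evaluated continuously, C8.2 has all medical events reported to OMSO, and C6.1 makes OMSO responsible for observing and monitoring them. That also stands, and it limits the loss to transient symptoms nobody volunteers.

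A reader might infer several stronger things that the documents do not support:

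- *At least 8 of 28 days are uncovered.* Eight is not a floor. Daily checks may begin inside week 4, and VO2peak visits after week 2 and in the last week could lower the count slightly if they fall on free days and count as prescribed exercise.
- *Rest-day symptoms are what is lost.* The worked examples show otherwise.
- *Injections would proceed unchecked.* Injection weekdays are not visible, and three injections fit easily within five exercise days.
- *Adverse-event comparisons would be biased.* B5.8.2 and the SAP plan no comparison of event rates between dosing and follow-up.

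**Conclusion.** The point holds as a limited gap in scheduled, solicited symptom capture. On the visible text, an ordinary dosing week leaves about 48 hours outside any questionnaire window. Over the phase that is about 6 to 8 of 28 day-equivalents, or about 12 if time trials carry no check.

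The size rests on three assumptions: prescribed exercise is the only trigger during dosing, the form is applied literally as worded, and no unseen timeline adds checks. If daily checks are in fact scheduled throughout, the gap vanishes and only the wording needs correcting.

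It is worth acting on because following the form as written gives poorer symptom capture than a one-line alternative. Neither unchecked injections nor biased safety results can be concluded from it.

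**What to change.** Change the Appendix A stem from a 24-hour look-back to *since your last questionnaire*. A volunteer's first form needs its own starting point, for which the present 24 hours will serve. Consecutive forms then join up, so the solicited-symptom gap between them is zero on any calendar, and on daily follow-up days the new stem asks about the same period as now. The cost is one line of text and slightly less precise recall when two or three days separate forms.

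This edit does not supply vital signs for days without a check. Separately, B5.3 (Erythropoietin Injections and Study Exercise) and C6.1 (Exogenous EPO) should be reconciled to state which injection-phase days carry the questionnaire and vital signs, and whether time-trial and VO2peak days count as prescribed exercise. They should also state the day on which daily follow-up begins. Which schedule is right is for the sponsor and the medical office to decide.

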Research-related Risks: Venipuncture is a routine clinical procedure the medical community commonly uses to obtain blood samples. The immediate complications may be slight pain during the entry of the needle into the skin, possible dizziness, and syncope. Dizziness or syncope constitutes no long-term harm, and immediate relief is achieved by having the subject put their head down between their knees or lie down. Additionally, a hematoma may result from the venipuncture, but this is more unsightly than risk producing. Late complications might include thrombosis of the vein due to trauma or infection. These complications are extremely rare.

Measures to Minimize Risks of Harm: Participant monitoring, aseptic technique, including sterile disposable blood collection apparatus and adherence to standard medical precautions reduce risk. Trained technicians will perform all venipuncture. Subjects will be briefed on the signs and symptoms of potential complications and given information on who to contact for medical assessment and/or treatment. Credentialed personnel performing venipuncture will be listed on the DOA log with code "S."

Research Procedure Name: Exogenous EPO

Research Procedure Description: A needle and syringe will be used to inject prescribed EPO amounts subcutaneously in the abdomen 3 times a week for 4 weeks.

Research-related Risks: Side effects with EPO injection are redness and pain at the site of injection, increase blood pressure, blood clots, joint pain, nausea, dizziness, headaches, trouble sleeping, and weight loss. Rare but possible side effects can include myocardial infarction and stroke

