quality. This also includes continuous evaluation of the following: recruitment, the informed consent process, adverse events, protocol adherence, and protocol deviations. This will occur continuously in order to identify unanticipated problems or risks to the volunteers associated with the research. The Principal Investigator will ensure that the number of volunteers recruited for this study complies with the protocol. If adverse events occur, the Principal Investigator will submit a monthly summary of the related adverse events to OMSO to determine whether the number of adverse events is excessive for the risks outlined in the research protocol. The Principal Investigator and Study Coordinator will be responsible for ensuring that the appropriate regulatory and IRB documentation is on file and up to date.

C8. REPORTABLE EVENTS

C8.1 Expected adverse events

An adverse event is defined as any untoward or unfavorable medical occurrence in a human research participant, including any abnormal sign (e.g., abnormal physical exam or laboratory finding), symptom, or disease, temporally associated with the individual's participation in the research, whether or not considered related to the individual's participation in the research.

Expected adverse events are local bruising and soreness from blood draws and at the site of EPO injections, and muscle soreness or pain from exercise. Expected adverse events for muscle biopsies are local soreness, redness, or bruising. Expected adverse events which are not serious are reported to the IRB at the time of continuing review of the protocol.

All medical events that the USARIEM Office of Medical Support and Oversight (OMSO) evaluates will be reported to the ORQC.

C8.2 Unexpected adverse events and unanticipated problems

A serious adverse event is any adverse event temporally associated with the subject's participation in research that is fatal, life-threatening, permanently disabling, requires inpatient hospitalization, or results in congenital anomalies/birth defect, overdose or cancer, or based on appropriate medical judgment, may jeopardize the participant, or may require medical or surgical intervention to prevent one of the above outcomes.

All medical events will be reported to USARIEM's Office of Medical Support and Oversight (OMSO). OMSO staff will retain a copy of the report in the subject's OMSO medical file as a means of tracking and analyzing trends in medical events.

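### The Appendix A symptom form cannot separate dizziness from sweating or fatigue after training, and has no specific item for joint pain or injection-site reactions

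*Protocol*

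**What the plan says.** Protocol C6.1 (Exogenous EPO) lists the side effects as "redness and pain at the site of injection, increase blood pressure, blood clots, joint pain, nausea, dizziness, headaches, trouble sleeping, and weight loss". The same entry places the injections in the abdomen: "A needle and syringe will be used to inject prescribed EPO amounts subcutaneously in the abdomen 3 times a week for 4 weeks". Section C8.1 adds: "Expected adverse events are local bruising and soreness from blood draws and at the site of EPO injections".

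The symptom form is Appendix A. Its stem is "Have you experienced in the last 24 hours any", followed by 15 items. Three matter here:

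- Item 3: "Dizziness, lightheadedness, clamminess, diaphoresis (sweating), or fatigue".
- Item 5: "Extremity swelling, pain, warmth, erythema".
- Item 14: an open-ended item on skin problems, with rash and blistering as examples.

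Under B5.3 (Erythropoietin Injections) and C6.1, volunteers complete the form and have vital signs checked before the day's prescribed exercise. Copies go to OMSO daily, and use of the form continues daily for two weeks after the last injection. B5.3 (Study Exercise) sets four training days and one time-trial day a week during dosing, with "exercise-induced energy expenditure being 1000-1500 kcal per day". Section C7.1 has the principal investigator send OMSO a monthly summary of related adverse events, if any occur, so that OMSO can judge whether their number is excessive for the risks the protocol describes.

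**The concern.** Item 3 puts a named drug effect in the same line as two ordinary consequences of hard training. The form is filled in before exercise and looks back 24 hours, so on consecutive exercise days most of the previous session lies inside the window. Nothing tells the volunteer to leave out symptoms that occurred only during exercise. An item that training alone can turn positive is a weak flag for dizziness and yields no count of it.

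The form also gives no prompt for pain at the injection site, although C6.1 and C8.1 both lead a reader to expect pain or soreness there, and no prompt that names joints. What is at stake is the quality of the safety record. OMSO's judgement under C7.1 needs counts that correspond to the named risks, and for these effects the form does not supply them.

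**Working it through.** The plan states no figure on this point, so there is none to reproduce. The check has three parts.

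**1. Named effects against form items** (C6.1 against Appendix A)

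- Headache: its own item (9).
- Nausea: item 4, pooled with other digestive symptoms.
- Dizziness: item 3 only, pooled with lightheadedness, clamminess, sweating and fatigue.
- Trouble sleeping: line 15d.
- Weight loss: line 15c, and body mass is measured weekly (B5.3, Height and Weights).
- Raised blood pressure: measured with the vital signs.
- Blood clots: covered indirectly by items 1, 2 and 5 to 7.
- Joint pain: no specific item. Item 5 could take pain in a limb joint, but it would also take training soreness, and it mixes pain with swelling, warmth and redness.
- Injection-site redness: no specific item. Item 14 could take it, but without attributing it to the injection site.
- Injection-site pain: no item. The abdomen is not an extremity, and item 14 concerns skin abnormalities.

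**2. How many forms look back on exercise**

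Inputs: 4 training days plus 1 time trial gives 5 exercise days a week (B5.3); 4 weeks of dosing; 8 volunteers (B5.2.2). Assumption: one form per exercise day. C1.3 bars additional exercise.

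- Dosing-phase forms: 5 × 4 × 8 = 160.
- Rest days per week: 7 − 5 = 2.
- If the rest days are adjacent, 1 of the 5 weekly forms follows a rest day and 4 follow an exercise day: 4 × 4 × 8 = 128.
- If the rest days are separate, 2 of the 5 follow a rest day and 3 follow an exercise day: 3 × 4 × 8 = 96.

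So 96 to 128 of the 160 forms follow an exercise day, and 160 − 128 = 32 to 160 − 96 = 64 follow a rest day. These are forms whose window covers a session, not forms on which item 3 would be positive.

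**3. What pooling costs at assumed rates**

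Let b be the proportion of forms with sweating, fatigue or another non-dizziness symptom of item 3, and d the proportion with dizziness. The documents give neither. Assuming independence and one yes/no answer per item:

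- P(item 3 positive) = 1 − (1 − b)(1 − d).
- Share of positives that include dizziness = d / P.

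With d = 10%:

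| b | P(item 3 positive) | Share with dizziness |
|---|---|---|
| 10% | 1 − 0.90 × 0.90 = 19% | 0.10/0.19 = 53% |
| 30% | 1 − 0.70 × 0.90 = 37% | 0.10/0.37 = 27% |
| 50% | 1 − 0.50 × 0.90 = 55% | 0.10/0.55 = 18% |
| 80% | 1 − 0.20 × 0.90 = 82% | 0.10/0.82 = 12% |
| 90% | 1 − 0.10 × 0.90 = 91% | 0.10/0.91 = 11% |

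At b = 50%, dizziness on one form in ten raises the positive rate by 5 percentage points (50% to 55%); at b = 80%, by 2 points (80% to 82%). A separate dizziness item would read 10% in every row. The loss depends on b, which is unknown here.

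**The case against.** The form is a safety screen, not an outcome instrument. No objective in B4 and no analysis in B5.8 or the SAP estimates symptom rates from it, so no planned estimate is biased. This stands.

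A dizzy volunteer still answers yes to item 3, so pooling costs specificity, not sensitivity. This also stands. A reader might infer that the trial would understate how often EPO causes dizziness, but a count of positive item 3 answers would, if anything, be too high. The loss is that dizziness cannot be counted on its own.

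A reader might also infer that item 3 will be positive on nearly every form. The documents do not support that. C6.1 (Exercise) says only that fatigue may occur and gives no rate; 32 to 64 of the 160 forms follow a rest day; and the two-week follow-up comes after the training phase.

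It would likewise be too strong to say that joint pain and injection-site reactions have no place on the form. Items 5 and 14 can take part of them; only injection-site pain has none. Weight and sleep do not belong in the criticism: body mass is measured weekly, and sleep has a line of its own.

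Other routes exist. Credentialed staff give every injection on site, C6.1 makes OMSO responsible for monitoring adverse events, and C8.2 requires all medical events to be reported to OMSO. These soften the point but do not remove it. No follow-up question is prescribed after a positive item 3, and injection-site pain depends on a volunteer mentioning it or a member of staff asking.

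Finally, with a single arm of 8, even a separate dizziness item could not attribute dizziness to EPO rather than to training. That is so, but a symptom must be recorded separately before it can be counted at all.

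**Conclusion.** The point holds as a minor weakness in safety data collection. Item 3 cannot separate dizziness from sweating or fatigue expected after training, and the form has no specific item for joint pain or injection-site reactions; pain at the abdominal injection site has no item at all.

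The number of forms affected cannot be stated. The most that the schedule supports is that about 96 to 128 of 160 dosing-phase forms follow an exercise day. This assumes one form per exercise day, all 8 volunteers completing dosing, and no exercise beyond that prescribed. The percentages for item 3 illustrate assumed rates and are not findings. They also assume one answer per item, and the available text of Appendix A shows no answer fields.

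The efficacy analyses are untouched, and the documents do not show that adverse events would go unreported overall.

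**What to change.** Revise Appendix A as follows:

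- Split item 3 into (a) dizziness, lightheadedness or clamminess, and (b) sweating or fatigue beyond that expected from the exercise done.
- Add one item for pain, redness or swelling at the injection site.
- Add one item for joint pain.
- Count these items separately in the monthly adverse event summary that C7.1 sends to OMSO.

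The cost is a one-page form revision and a few seconds more per form. No dose, schedule, visit or planned analysis changes.
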